Study Title: “Best Practice Alert for Opioid Prescribing” NCT04446975

09/01/2022

Study Protocol and Statistical Analysis Plan

The study is a randomized multiple crossover cluster trial to evaluate a real-time best practice alert embedded into the electronic health record. Our clusters are an academic medical center and three community hospitals, all part of the University of Colorado Health system, which serves both inner-city and rural populations. Primary study subjects are credentialed prescribing providers at each site. Eligible secondary study subjects are postsurgical hospital inpatients who are hospitalized at least one night prior to discharge. There are no exclusion criteria for the prescribing providers. The exclusion criteria for eligible patients is being less than 18 years of age.

During the eight-week periods when prescriber alerts are active, providers that attempt to prescribe higher-than-optimal doses are automatically notified on the order screen with a suggestion for a recommended dose. In the subsequent eight-week period, there is no best practice alert available to trigger. The four hospitals are randomized to the alert starting configuration (ON vs. OFF) in alternating clusters between best practice alert ON and OFF conditions for four eight-week periods, each separated by a four-week washout interval to minimize learning and augment masking. Randomization is implemented, so investigators and data analysts remain masked to the condition designation. While providers are exposed to the alerts during active periods if their prescription triggers a best practice alert, the schedule was not shared with providers or patients.

Baseline characteristics balance is assessed using absolute standardized difference calculated as the difference in means or proportions divided by the pooled standard deviation. An absolute standardized difference > 0.1 was considered to indicate an imbalance. The analysis is conducted at the individual patient level using a modified intention-to-treat strategy. The effect of the best practice alert on opioid prescription at discharge is evaluated using a linear regression model.

We determined that it would be feasible to recruit 1,500 patients per cluster period across four hospitals for four time periods. Although we considered a 33.3% reduction of prescribed opioids a clinically meaningful reduction for prescriptions “exposed” to the best practice alert, we utilized a smaller effect size (11.1% reduction) for the power analysis to incorporate the average effect across all patients. We estimated that the trial would have $>99\%$ power to detect a ratio of geometric means of 0.89 (ON/OFF) for the amount of prescribed opioids or a difference of -0.12 (ON – OFF) on the log-scale, at the 0.05 significance level.

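### The alert model has no term for the prescriber, who is the trial's primary subject; shifts in prescriber mix add avoidable variance that ordinary regression standard errors understate

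*Combined protocol and SAP*

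**What the plan says.** The first paragraph of the combined protocol and SAP sets the hierarchy: "Primary study subjects are credentialed prescribing providers at each site", with postsurgical inpatients as secondary subjects. The second paragraph has the electronic record notify a provider on the order screen when an attempted dose is above the optimal one. Hospitals are randomized to their starting configuration, with "alternating clusters between best practice alert ON and OFF conditions for four eight-week periods", and neither providers nor patients were given the schedule.

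The analysis paragraph states: "The analysis is conducted at the individual patient level using a modified intention-to-treat strategy". It then names a linear regression for the alert effect on discharge opioid prescription. It lists no covariates, no hospital, period or prescriber terms, and no clustered or robust variance.

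The sample-size paragraph gives an effect of "a difference of -0.12" on the log scale, tested "at the 0.05 significance level", with power above 99%. It gives no SD, intraclass correlation, number of prescribers or turnover.

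**The concern.** The alert can work only by changing what a prescriber orders, and prescribers differ in how much they habitually order. Hospitals cross over, but the people signing discharge orders need not be the same, or equally busy, in each of four eight-week periods spread over 4×8 + 3×4 = 44 weeks. This variation occurs within a hospital from one period to the next, so hospital and period terms cannot absorb it.

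Two things are at stake. The estimate is noisier than it need be, because the within-prescriber ON/OFF contrast that the crossover offers is not used. And an ordinary regression standard error treats patients of the same prescriber as independent, so it is too small and the test rejects a true null too often.

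**Working it through.** **1. The plan's power figure.** ln 0.89 = −0.117, which rounds to the stated −0.12. The plan says "it would be feasible to recruit 1,500 patients per cluster period across four hospitals for four time periods". Read as 1,500 per hospital-period, N = 1,500×4×4 = 24,000. Read as 1,500 per period over all four hospitals, N = 1,500×4 = 6,000, or 375 per hospital-period. Ignoring clustering, with half the patients in each condition, SE = SD×√(4/N). Two-sided power is Φ(0.12/SE − 1.96); sidedness is not stated.

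- At SD 1 (assumed), SE = 0.0129 for N = 24,000 and 0.0258 for N = 6,000. In the second case power = Φ(4.65 − 1.96) = 99.6%.
- 99% power needs SE ≤ 0.12/(1.960 + 2.326) = 0.0280, so SD ≤ 2.17 (N = 24,000) or ≤ 1.08 (N = 6,000).
- At SD 1, the claim of more than 99% therefore tolerates a variance inflation of about 4.7 or 1.18.

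The figure cannot be strictly reproduced without an SD, but it is attainable if clustering is ignored.

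**2. Bias or noise?** The 4-hospital by 4-period alternating design was simulated under no alert effect. Assumptions: total SD 1; 50 or 150 prescribers per hospital; prescriber share 0.05 to 0.30; 0% or 20% turnover per period; volumes varying between periods; hospital and period terms fitted; 500 replicates per setting. The mean estimate stayed within 0.002 of zero in every setting at N = 24,000. The largest departure at N = 6,000 was 0.0047, under three simulation standard errors (0.0394/√500 = 0.0018). No systematic shift appears.

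**3. Standard error without a prescriber term (same simulation).**

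| N | true variance / model variance | type I error, no prescriber term | type I error, prescriber fixed effects |
|---|---|---|---|
| 24,000 | 1.4–10.3 | about 9%–55% | about 3%–7% |
| 6,000 | 1.1–3.5 | about 7%–31% | about 3%–7% |

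At lower prescriber shares (0.02 to 0.10), a separate run at N = 24,000 gave 6%–36% without the term.

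**4. Variance saved by a prescriber intercept.** Hospital and period terms are in both models, and variance components are taken as known. Assumptions: SD 1, two hospitals starting ON and two OFF, 60 or 150 prescribers per hospital with uneven volumes, 10% or 30% turnover per period. Entries are variance with the term divided by variance without it.

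| prescriber share | 1,500 per hospital-period | 375 per hospital-period |
|---|---|---|
| 0.02 | 0.69–0.87 | 0.92–0.99 |
| 0.05 | 0.48–0.71 | 0.78–0.92 |
| 0.10 | 0.29–0.53 | 0.59–0.84 |

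Example (share 0.05, 60 prescribers, 30% turnover, 1,500): the SD of the alert estimate falls from 0.0214 to 0.0149, a ratio of 0.0149²/0.0214² = 0.000222/0.000458 = 0.48. An independent re-simulation gave 0.0199 falling to 0.0137. The saving depends partly on workload that fluctuates. With turnover only and constant expected volumes, the ratios at 1,500 were 0.85–0.97, 0.59–0.95 and 0.42–0.76.

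**5. Other hospital-by-period variance.** With alert coded ±½ over 16 balanced cells, the sum of squares is 16×¼ = 4. A hospital-period variance share s therefore adds about s/4 to the variance of the alert effect, with or without a prescriber term. For the example:

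- s = 0.001: (0.000222 + 0.00025)/(0.000458 + 0.00025) = 0.67
- s = 0.005: (0.000222 + 0.00125)/(0.000458 + 0.00125) = 0.86
- s = 0.01: (0.000222 + 0.0025)/(0.000458 + 0.0025) = 0.92

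The re-simulation gave 0.66 and 0.91 for the first two. Across the assumed range, s = 0.005 leaves ratios of about 0.7 to 1.0.

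**The case against.** Three stronger readings are tempting, and the documents support none of them.

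- A reader might infer that prescribers deliver the intervention. They do not: the record system issues the alert automatically and prescribers receive it. The case for the term rests on their being the recipients and the source of the outcome.
- A reader might infer that the plan chose to ignore the prescriber. It lists no model terms at all, so the gap is an unspecified model.
- A reader might infer that changes in prescriber mix bias the comparison. With a randomized start and an undisclosed schedule, nothing in the documents makes the mix follow the ON/OFF condition. Imbalance in one realized trial is sampling error that a correct standard error would cover.

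The strongest remaining case is that this is an efficiency gain the trial may not need. In the example, 0.12/0.0214 = 5.6, so power exceeds 99% without the term. That stands for the example, which has no other hospital-period variance. It does not carry over to N = 6,000, where only 1.18-fold inflation is affordable at SD 1 and the simulated inflation was 1.1 to 3.5. Nor does high power protect against false positives from a standard error that is too small.

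Two further objections stand. A cluster-aware variance at the hospital-period level would by itself allow for random mix variation, at the price of a wider interval. And the prescriber intercept has costs. The estimate leans more on prescribers seen in both conditions, so learning that outlasts the washout could attenuate it somewhat more. Patients are also reweighted across prescribers, whereas the power calculation concerns an average over all patients: "we utilized a smaller effect size (11.1% reduction) for the power analysis to incorporate the average effect across all patients".

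**Conclusion.** The point holds as one of precision and valid standard errors, not of bias. No prescriber term is stated although prescribers are the primary subjects, and adding one is a cheap improvement.

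Its size cannot be fixed from the documents. Under the assumptions in step 4, the variance of the alert effect falls to roughly 0.3–0.9 of its value with 1,500 patients per hospital-period and 0.6–1.0 with 375, provided there is no other hospital-period variance. With a hospital-period share of 0.005 it falls only to about 0.7–1.0. A large gain should therefore not be promised. Ordinary standard errors were too small in every setting of step 3. The prescriber term cures that only if prescriber mix is the sole source of hospital-period variation, which is why inference at the hospital-period level is needed as well.

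**What to change.** In the analysis paragraph, write out the alert model:

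- alert condition, hospital and period terms, plus a random intercept for the responsible discharging provider;
- one definition of that provider for every patient, whether or not an opioid was ordered. Using the signer when an order exists and someone else otherwise would tie the definition to an event the alert can affect;
- inference at the hospital-period level, for example through a hospital-by-period random effect with the alert coefficient referred to 16 − 1 − 3 − 3 − 1 = 8 degrees of freedom;
- the model without the prescriber term as a sensitivity analysis, and prescriber mix reported by condition.

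A random intercept is preferable to fixed effects, which can lose precision when prescribers are many and patients few. In the step 2 simulation with 375 per hospital-period, 150 prescribers, share 0.05 and 20% turnover, the true SE was 0.0309 with fixed effects against 0.0274 with no prescriber term.

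The cost is a few sentences and one or two model terms. The alert responds to an individual provider's order, so that provider should be identifiable in the record. That a responsible discharging provider is also recorded for patients with no opioid order is an assumption to confirm. The possible extra attenuation from learning and the reweighting of patients are the price, and the sensitivity analysis lets readers judge them.

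### Does the crossover plan need an analysis for carry-over of learning from alert-ON into alert-OFF periods?

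*Combined protocol and SAP*

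**What the plan says.** The design paragraph of the combined protocol and SAP sets out "alternating clusters between best practice alert ON and OFF conditions for four eight-week periods, each separated by a four-week washout interval to minimize learning". A second safeguard follows: "the schedule was not shared with providers or patients". Each hospital's starting condition is randomized, but the split is not stated.

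The analysis paragraph works at patient level under modified intention-to-treat and says: "The effect of the best practice alert on opioid prescription at discharge is evaluated using a linear regression model". It names no covariates, so it has no hospital, period or carry-over term.

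The sample-size paragraph powers the trial for a "difference of -0.12 (ON – OFF) on the log-scale, at the 0.05 significance level" and claims power above 99%. On the size of effect: "we utilized a smaller effect size (11.1% reduction) for the power analysis to incorporate the average effect across all patients". It gives no standard deviation and no intracluster correlation.

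**The concern.** The alert shows prescribers a recommended dose, and a prescriber can remember it after the alert is switched off. Hiding the schedule does not undo that. Under strict alternation most of the OFF experience comes after an ON period, so the comparator may already be partly treated. Only period 1 offers OFF data from hospitals that have never been exposed. A reader used to crossover trials therefore looks for a carry-over term or sensitivity analysis and finds none.

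At stake would be the size of the estimate. The plan states that "we considered a 33.3% reduction of prescribed opioids a clinically meaningful reduction for prescriptions" exposed to the alert, and it translates this into 11.1% across all patients. If learning dilutes the contrast, an alert that truly reaches that level could be reported as falling short, and a small result could not be told apart from learning.

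**Working it through.** **Inputs from the documents.** Four hospitals, four alternating periods (16 hospital-periods), a four-week washout, a ratio of 0.89 or -0.12 on the log scale, alpha 0.05, power above 99%.

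**Assumptions.** Two hospitals start ON and two OFF, hospitals are of equal size, tests are two-sided. L is the fraction of the effect θ that outlasts the washout. The documents give no value for L.

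**The plan's own figures.** ln 0.89 = -0.1165 and ln(1 - 0.111) = -0.1177. Both round to -0.12. The stated power can be matched only conditionally. With independent patients the SD must not exceed 0.12 / [(1.960 + 2.326) × √(2/n)], with n patients per condition. The sentence on 1,500 patients can mean 6,000 in total (n = 3,000), which gives SD ≤ 1.08, or 24,000 (n = 12,000), which gives SD ≤ 2.17.

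**Case A: learning shows only in OFF periods that follow ON.** The 8 ON hospital-periods average θ. Of the 8 OFF hospital-periods, 6 carry Lθ and 2 carry nothing, so they average 0.75Lθ. The estimate is θ(1 - 0.75L):
- L = 25%: -0.12 × 0.8125 = -0.0975, ratio 0.907
- L = 50%: -0.12 × 0.625 = -0.075, ratio 0.928

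Without period terms the coefficient is 0.625 if one hospital starts ON (5 of 8), 0.875 if three do (7 of 8), and 1 if all four do.

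**Case B: learning persists and adds to the alert in later ON periods as well, without accumulating.** Hospitals starting ON have effects θ, Lθ, θ(1 + L), Lθ. Hospitals starting OFF have 0, θ, Lθ, θ(1 + L).
- ON mean: θ(1 + 0.5L)
- OFF mean: 0.75Lθ
- Estimate: θ(1 - 0.25L)

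At L = 50% this is -0.12 × 0.875 = -0.105. The bias is one third of that in case A, and the documents cannot say which case applies.

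**Case C: rebound.** If prescribing rises after switch-off by 25% of the effect, the estimate is -0.12 × (1 + 0.75 × 0.25) = -0.1425, an overstatement. Carry-over need not shrink the effect.

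**Type I error.** An alert with no effect has nothing to carry over, so this mechanism creates no false positive.

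**What the usual remedy would do.** Add a term for the previous condition. With no other terms, the treatment estimate becomes the mean of the 8 ON hospital-periods minus the mean of the 2 never-exposed OFF ones. With s² the variance of one hospital-period mean, its variance is s²/8 + s²/2 = 0.625s², against s²/8 + s²/8 = 0.25s² unadjusted, a factor of 2.5. Least squares on the 16 means gives the other rows:

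| Other terms | Variance factor | Estimate, case A | Estimate, case B |
|---|---|---|---|
| none | 2.5 | θ | θ(1 + 0.5L) |
| hospital | 2.8 | θ | θ(1 + 0.5L) |
| period | 4.0 | θ | θ |
| hospital and period | 5.5 | θ | θ(1 - 0.25L) |

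In case B at L = 50%, the model without period terms gives -0.12 × 1.25 = -0.15, further from -0.12 than the unadjusted -0.105 and in the inflating direction. With both hospital and period terms the bias equals the unadjusted one, at 5.5 times the variance. If all four hospitals start alike, the previous-condition term cannot be estimated separately.

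**The case for a change.** The strongest case for acting is that the omission is real and the remedy cheap: one extra model and one sentence of caution, on data already collected. The estimate could also be misread against the plan's benchmark. Since 33.3 / 11.1 = 3, a case A estimate at L = 25% or 50% would read as about 9.3 × 3 = 28% or 7.2 × 3 = 22% for exposed prescriptions, short of 33.3%.

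Power could suffer too. If power is exactly 99% without carry-over, case A leaves about 94% at L = 25% and 77% at L = 50%. From 99.9% it leaves about 98% and 89%. So it cannot be said in general that the test is little affected.

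What stands is that the plan names no carry-over analysis, and that same-direction learning would dilute the estimate and cost some power. The rest is weaker:
- The plan uses 33.3% and 11.1% for planning power. Nothing says that the result will be judged against them.
- The shortfall depends partly on the scaling. Multiplying by three on the log scale gives 1 - exp(-0.36) = 30% with no carry-over at all, then 25% and 20%.
- The power losses rest on assumed values of L.
- The remedy helps only if the form of learning is known, as the table shows.

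**Conclusion.** The concern does not hold. The plan recognises learning and deals with it through the washout and the undisclosed schedule, which is a legitimate choice. Its documents contain no contradiction on this point and no evidence that learning outlasts four weeks.

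The possible bias with 2:2 starts runs from 0.25L to 0.75L of the effect towards zero, and it reverses sign under rebound. L is unknown throughout. A previous-condition model could correct this, do nothing, or overstate the effect, at 2.5 to 5.5 times the variance. Whether to add such a model or a sentence of caution is for the sponsor to decide. Neither would change the primary analysis or its result.

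These figures rest on equal hospital sizes, 2:2 starts unless stated otherwise, and the simple forms of learning set out above. That the regression names no hospital or period terms is a separate matter, and a carry-over term could only be considered once those are settled.

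### Does the plan need to say what follows when a baseline characteristic crosses the 0.1 balance cut-off, and which characteristics enter the regression?

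*Combined protocol and SAP*

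**What the plan says.** The analysis paragraph of the combined protocol and SAP (its sections are unnumbered) gives baseline characteristics one use. It defines the measure, "Baseline characteristics balance is assessed using absolute standardized difference calculated as the difference in means or proportions divided by the pooled standard deviation", and then the cut-off, "An absolute standardized difference > 0.1 was considered to indicate an imbalance". The characteristics are not listed, and nothing is said to follow from crossing the line.

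The same paragraph sets the level of analysis, "The analysis is conducted at the individual patient level using a modified intention-to-treat strategy", and the model: "The effect of the best practice alert on opioid prescription at discharge is evaluated using a linear regression model". No covariate, hospital term or period term is named.

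On the design: "Our clusters are an academic medical center and three community hospitals", and "The four hospitals are randomized to the alert starting configuration (ON vs. OFF) in alternating clusters". There are four eight-week periods. The same text says that investigators and analysts are kept masked to which condition is which. The sample size paragraph adds "We determined that it would be feasible to recruit 1,500 patients per cluster period across four hospitals for four time periods" and the target, a "ratio of geometric means of 0.89 (ON/OFF) for the amount of prescribed opioids", equated to -0.12 on the log scale.

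**The concern.** A threshold with no consequence invites the question of what it is for. If a characteristic exceeds 0.1, the analyst could ignore it, add it to the regression, or add it only as a sensitivity analysis, and the text does not choose.

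The design sharpens the question. Alternation within each hospital largely balances stable differences between hospitals. It does not balance a change in surgical case mix from one eight-week period to the next. If every hospital alternates, there are 8 ON and 8 OFF hospital-periods, and chance differences at that level do not shrink to near zero as more patients are enrolled.

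At stake would be a conditional shift in this trial's estimate, some lost precision, and a primary estimate that depends on covariates picked after the balance table has been seen.

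**Working it through.** **Inputs from the documents.** Four hospitals, four periods, cut-off 0.1, log-scale target 0.12, alpha 0.05, power above 99%. The 1,500 can be read as patients per hospital-period (24,000 in all) or per period over four hospitals (6,000 in all, m = 375 per hospital-period). Both readings are carried.

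**Assumptions, because the documents give no value.** Log-scale SD 1; covariate-outcome correlation r = 0.2 to 0.4; a share g of the covariate's variance lying between periods within a hospital; equal-sized hospital-periods, 8 per condition; two-sided test.

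**The plan's own figures.** ln(0.89) = -0.117 and exp(-0.12) = 0.887, so the two statements of the effect agree after rounding. Power above 99% cannot be reproduced without an SD or a within-cluster correlation. With independent patients it holds for an SD up to about 1.08 (3,000 per condition) or 2.17 (12,000 per condition).

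**Step 1: shift if a covariate sits exactly at the cut-off.** Shift = 0.1 × r × SD. For r = 0.2 this is 0.02 (17% of 0.12); for r = 0.4 it is 0.04 (33%). Widening to SD 0.5 to 1.5 and r 0.1 to 0.5 gives 0.005 to 0.075 (4% to 63%). These figures apply only if 0.1 is reached.

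**Step 2: how large chance differences are.** SD of the standardized difference = sqrt(2 × (g/8 + (1 - g)/(8m))). For g = 0.01 and m = 1,500: sqrt(2 × (0.00125 + 0.0000825)) = 0.0516. The typical (one-SD) shift is that value × r × SD.

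| g | m | SD of standardized difference | Chance of exceeding 0.1, per variable | Typical shift, r = 0.2 to 0.4 | Share of 0.12 |
|---|---|---|---|---|---|
| 0 | 1,500 | 0.0129 | below 0.0001 | 0.003 to 0.005 | 2% to 4% |
| 0 | 375 | 0.0258 | 0.0001 | 0.005 to 0.010 | 4% to 9% |
| 0.005 | 1,500 | 0.0376 | 0.8% | 0.008 to 0.015 | 6% to 13% |
| 0.005 | 375 | 0.0437 | 2.2% | 0.009 to 0.017 | 7% to 15% |
| 0.01 | 1,500 | 0.0516 | 5.3% | 0.010 to 0.021 | 9% to 17% |
| 0.01 | 375 | 0.0562 | 7.5% | 0.011 to 0.022 | 9% to 19% |
| 0.02 | 1,500 | 0.0719 | 16% | 0.014 to 0.029 | 12% to 24% |
| 0.02 | 375 | 0.0752 | 18% | 0.015 to 0.030 | 13% to 25% |

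So the shifts in Step 1 are the unlikely end, and without drift they practically do not occur.

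**Step 3: bias.** A 20,000-run simulation of four alternating hospitals with hospital and period terms (g = 0.01, m = 1,500, covariates explaining 25% of the variance) gave a mean unadjusted error of -0.0006. There is no systematic bias; the shifts above are part of ordinary sampling error.

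**Step 4: precision gained by adjusting.** Here g is the outcome's hospital-period share. Adjusted SE = sqrt(2 × ((1 - q) × g/8 + (1 - R²) × (1 - g)/(8m))), where R² and q are the shares of patient-level and hospital-period variance explained.

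- q = R² = 0.10, 0.20 or 0.30: the SE is multiplied by sqrt(0.90), sqrt(0.80) or sqrt(0.70), a cut of 5%, 11% or 16%.
- R² = 0.25 and q = 0, with g = 0.01 and m = 1,500: 0.0516 falls to 0.0512, a cut of 0.8%. Over g = 0.005 to 0.02 and both values of m the cut is 0.4% to 4%.
- With g = 0, R² = 0.25 gives a cut of 1 - sqrt(0.75) = 13%, but of an SE that is only 0.0129 or 0.0258.

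**Step 5: what the gain would buy.** Power of 99% for 0.12 implies an SE of at most 0.12/(1.960 + 2.326) = 0.028, where a further cut changes little. If the SE were 0.0516 instead, power would be about 64%, and a 5% to 16% cut would raise it to about 69% to 79%. That is useful, but the main difficulty would then be hospital-period clustering.

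**The case for a change.** The best case for a change is this. The gap is real on the face of the text: a cut-off without a consequence and a regression without terms. The usual reassurance that large samples balance out is weak here, because 8 hospital-periods per condition set the limit. Several characteristics are presumably checked, so the per-variable chances add up. Fixing a short covariate list before unmasking would cost only wording and would remove a data-driven choice, even if the precision gain were small.

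The textual point stands, and so does the point about few hospital-periods. The rest weakens on inspection. Nothing in the documents indicates how much case mix drifts between eight-week periods, so the size rests on an assumed g. The covariate list cannot be named from the documents, which mention no baseline characteristic and do not say whether any is prognostic. The masking of analysts does not stop a covariate being chosen after an imbalance is seen, but it limits steering towards a preferred direction. A descriptive balance check alongside an effect model without covariates is also a legitimate analysis of a randomized trial, so adjusting is a choice about efficiency.

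**Conclusion.** No change to the plan follows. The plan is silent on whether baseline characteristics enter the effect model. That is missing detail, which analysts can settle sensibly before unmasking by treating the 0.1 flag as description and choosing any covariates on prognostic grounds.

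The silence does not bias the estimate. With SD 1, correlation 0.2 to 0.4, 1,500 patients per hospital-period and 0.5% to 1% of covariate variance between periods, one covariate typically moves the estimate by about 0.01 to 0.02 (6% to 17% of 0.12). Without drift the figure is 2% to 4%, and several covariates could add up. Shifts of 17% to 33% need a covariate to reach the cut-off. The chance of that is about 0.0001 or less per variable without drift, and 0.8% to 18% under the assumed drift.

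The precision gain, 0.4% to 16% when hospital-period variance is present, depends on what the covariates explain at the hospital-period level, which the documents cannot show. How the regression represents hospital, period and clustering is the larger open question about this model, and a covariate list would not answer it.

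### Four hospitals are randomised over 16 hospital-periods, but the only stated effect analysis is a patient-level linear regression with no hospital-period component, clustered variance or small-sample degrees of freedom named

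*Combined protocol and SAP*

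**What the plan says.** The combined protocol and SAP has no numbered sections, so places are given by paragraph.

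- **Design (opening paragraphs).** "The study is a randomized multiple crossover cluster trial to evaluate a real-time best practice alert embedded into the electronic health record". The randomised units are named directly after this, and there are only four of them: "Our clusters are an academic medical center and three community hospitals". Each hospital is randomised to begin with the alert on or off, then alternates for four eight-week periods with washouts between them.
- **Analysis (last paragraph on analysis).** "The analysis is conducted at the individual patient level using a modified intention-to-treat strategy". The next sentence is the whole of the effect model: "The effect of the best practice alert on opioid prescription at discharge is evaluated using a linear regression model".
- **Sample size and power (final paragraph).** "We determined that it would be feasible to recruit 1,500 patients per cluster period across four hospitals for four time periods". On the effect: "we utilized a smaller effect size (11.1% reduction) for the power analysis to incorporate the average effect across all patients". Power above 99% is claimed at the 0.05 level for a log-scale difference of -0.12. The SD and any intracluster or hospital-period correlation are not given.

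Nowhere do the documents name a hospital, period or hospital-period term, a random effect, a clustered variance or a rule for degrees of freedom.

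**The concern.** The alert is either on or off for a whole hospital-period. The information about its effect therefore comes from comparing 16 hospital-periods in four hospitals, not from thousands of independent discharges.

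Three sources of variation need to be kept apart:

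- **Stable differences between hospitals** (usual prescribers, usual case mix) cancel in a balanced within-hospital crossover.
- **Calendar effects common to all hospitals** are removed by period terms, if these are fitted.
- **Hospital-specific change from period to period** is removed by neither. Examples would be a staffing or case-mix shift at one site in one period. It moves every patient in that hospital-period together.

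A patient-level regression that takes residuals as independent counts the third source as if it averaged out over all patients. Its intervals are then too narrow and the 0.05 level is not held. With hundreds of patients per hospital-period, a very small variance share is enough. The documents give no figure from which a reader could judge whether that share is negligible.

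**Working it through.** **Inputs from the documents.** 4 hospitals × 4 periods = 16 hospital-periods, 8 on and 8 off. The significance level is 0.05 (two-sided assumed, as it is not stated). The effect is -0.12 on the log scale; ln 0.89 = -0.117. The sample-size sentence can be read in two ways: m = 1,500 per hospital-period (16 × 1,500 = 24,000 patients), or 1,500 per period over four hospitals (m = 375, 6,000 patients). Both are carried through.

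**Assumptions.** The hospital-period share of variance (d) and the log-scale SD are not in the documents, so the values below are illustrations, not bounds. The simulations also assume equal cells, a 2:2 split of starting conditions and a between-hospital share of 0.02.

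**1. The plan's own power figure.** It cannot be reproduced without an SD. With independent patients, the largest SD that gives 99% power is 0.12 / [(1.960 + 2.326) × √(2/n)], where n is the number per condition:

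- n = 3,000: 0.12 / (4.286 × 0.02582) = 1.08
- n = 12,000: 0.12 / (4.286 × 0.01291) = 2.17

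**2. Type I error of the patient-level regression.** Design effect DE = 1 + (m − 1)d; error = 2 × [1 − Φ(1.96/√DE)].

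| d | DE, m = 375 | Error | DE, m = 1,500 | Error |
|---|---|---|---|---|
| 0 | 1 | 5.0% | 1 | 5.0% |
| 0.001 | 1.374 | 9.5% | 2.499 | 21.5% |
| 0.005 | 2.870 | 24.7% | 8.495 | 50.1% |
| 0.01 | 4.740 | 36.8% | 15.99 | 62.4% |

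Simulation of the 4 × 4 crossover agrees: at d = 0.001, 9.1–9.5% (m = 375) and 21.3–21.6% (m = 1,500) with condition only.

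The share that doubles the error to 0.10 is [(1.960/1.645)² − 1]/(m − 1) = 0.420/374 = 0.0011, or 0.420/1,499 = 0.0003.

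**3. Adding hospital and period fixed effects at patient level.** At d = 0.001 the simulated error is about 9.7% and 22%, and at d = 0.01 about 37% and 63%. These terms do not help with hospital-period variance.

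**4. Regression of the 16 means.** Degrees of freedom = 16 − (1 intercept + 1 condition + 3 hospital + 3 period) = 8. Simulated error is 4.9–5.1% at every share tried. A mixed model with a random hospital-by-period effect and t on 8 df is not the same test. At d = 0 it rejects in about 1.5% of trials. At d = 0.001 it rejects in 2.7% (m = 375) or 4.4% (m = 1,500).

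**5. If the alert effect differs by hospital.** With hospital-by-condition variance d in each condition plus hospital-period variance d/2, for d = 0.001 to 0.01:

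| Analysis | m = 375 | m = 1,500 |
|---|---|---|
| Patient-level, condition only | 0.16–0.54 | 0.37–0.75 |
| 16 means, 8 df | 0.09–0.17 | 0.14–0.19 |
| Four hospital differences, 3 df | about 0.05 | about 0.05 |

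**6. Interval width and power on 8 df.** Var = SD² × [d + (0.98 − d)/m]/4.

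- At SD 1, the 95% half-width at d = 0 / 0.001 / 0.005 / 0.01 is 0.029 / 0.047 / 0.087 / 0.119 with m = 1,500, against 1.96 × 2/√24,000 = 0.025 for independent patients. With m = 375 it is 0.059 / 0.069 / 0.101 / 0.129, against 0.051.
- At d = 0.01, power for -0.12 at SD 0.5 / 1 / 1.5 is 0.98 / 0.53 / 0.28 (m = 1,500) or 0.96 / 0.47 / 0.24 (m = 375).

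**The case against.** The strongest reply is that this is an omission, not a stated wrong method. The plan does not say ordinary least squares, condition only or independent patients. A linear regression can carry hospital terms and a clustered or mixed variance. The document shows that it knows the design is clustered: it calls the trial a cluster trial and counts patients by cluster period. This stands in part. A reader might infer that the trial will be, or was, analysed as if patients were independent, and the documents do not establish that. They do leave the variance model open, and the choices it permits have very different error rates.

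Second, the variance share is assumed. That stands in full. At a share of 0 the level is 5%, and no quoted error rate describes this trial.

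Third, the crossover already removes most clustering. This is right for stable hospital differences, and for shared calendar effects once period terms are fitted. It does not reach hospital-specific change over time.

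Fourth, the 8-df analysis is not safe in every case. This also stands. It runs at about 0.09–0.20 if the effect varies by hospital, which is plausible with one academic and three community sites. It is still much closer to 0.05 than the patient-level regression in the same setting.

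**Conclusion.** The point holds as a gap in the only stated effect test of a four-cluster trial, and it should be closed before the masked condition codes are opened. Followed as written, with nothing added, the regression gives intervals that are too narrow whenever hospital-specific period-to-period variance exists. How much too narrow is unknown, because the documents give no variance share and leave the cell size open to two readings. The illustrative type I error runs from 5% at a share of 0 to 37% (375 per cell) or 62% (1,500 per cell) at 0.01. These figures assume equal cells, independent hospital-period effects and a two-sided test.

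A reader might also infer that the claim of more than 99% "power to detect a ratio of geometric means of 0.89 (ON/OFF) for the amount of prescribed opioids" is wrong. The documents do not support that. The low powers shown above combine an assumed share with an assumed SD, and at a small SD or a small share the claim can hold. The figure cannot be verified, but it is not shown to be wrong.

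**What to change.** If the intended regression already contains suitable terms, write them into the SAP. Otherwise:

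1. **Name one primary model.** Regress the 16 hospital-period means on condition, hospital and period, with t on 8 df. Say that it assumes a common alert effect and that both starting conditions occur. If all four hospitals started alike, condition could not be separated from period; under independent coin tosses that has probability 2 × (1/2)⁴ = 1/8. The mixed model with a random hospital-by-period effect is an alternative, not an equivalent: it is conservative (about 0.015–0.03) when the share is near zero and cells are small.
2. **Add a sensitivity analysis** of the four within-hospital on-minus-off differences with t on 3 df, in case the effect varies by hospital. Common period shifts cancel in their mean only if the starting conditions split 2:2, so state the split.
3. **State the weighting.** Unweighted means count hospitals equally. The power paragraph speaks of an average over patients.
4. **State the SD, hospital-period variance and cell size** behind the power figure, and restate power for the chosen model.

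**Cost.** SAP wording and minor programming, with no extra data. Intervals widen: at SD 1 the half-width goes from 0.025 to 0.029–0.119 (1,500 per cell) or from 0.051 to 0.059–0.129 (375) over shares 0–0.01. The stated power may fall. The 3-df analysis has less power still: at share 0.01, 0.86 / 0.37 / 0.20 (1,500) or 0.80 / 0.32 / 0.17 (375) for SD 0.5 / 1 / 1.5. The estimate may also shift if the weighting changes from patients to hospitals.
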